1. STUDY OBJECTIVES

Study outcomes are measured at three different times, namely early post surgery period, 2 years of age and 5 years of age. This statistical analysis plan will focus on the outcomes measured at 5 years chronological age.

1.1. PRIMARY OBJECTIVE

The primary aim of this prospective, observer blind, randomised, multi-site, controlled, clinical, equivalence trial is to determine whether different types of anaesthesia (regional vs general) given to infants undergoing inguinal hernia repair result in equivalent neurodevelopmental outcomes at 5 years of age.

1.2. SECONDARY OBJECTIVES AT 5 YEARS

The secondary objective is to compare a range of secondary neurodevelopmental measures between groups at 5 years of age.

2. BACKGROUND/INTRODUCTION

2.1. STUDY DESIGN

The study is a prospective, observer blind, multi-site, randomised, controlled, equivalence trial. There are a total of 28 sites from seven countries. Participants are randomised in a 1:1 ratio to receive either regional anaesthesia (RA) or general anaesthesia (GA) during surgery for hernia repair. Randomisation is stratified by gestational age at birth and by site, giving a total of 52 strata.

Participants are infants scheduled for unilateral or bilateral inguinal hernia repair at one of the participating sites, identified through review of planned theatre schedules. The duration of participation was five years. Infants were enrolled before surgery. Data were collected before and during anaesthesia and in the early post-operative period (up to 5 days following the surgery). Formal neurodevelopmental assessments occurred at 2 years corrected age and 5 years chronological age.

2.2. TREATMENT GROUPS AND INTERVENTION

The GA group received sevoflurane for induction and maintenance. The airway could be maintained with a face mask, laryngeal mask or endotracheal tube, with or without neuromuscular blocking agents. Analgesia can be supplied with a caudal and/or ilioinguinal nerve block with bupivacaine or levo-bupivacaine up to a maximum dose of 2.5 mg/kg.

The RA group received no sedative agents. The regional blockade may be with spinal block alone, spinal block with caudal block, spinal with ilioinguinal block or caudal alone. A maximum dose of 2.5 mg/kg of bupivacaine or levo-bupivacaine can be used.

2.3. STUDY POPULATION

The planned study population comprised 660 infants of postmenstrual age 60 weeks or less, requiring inguinal hernia repair under anaesthesia. Exclusion criteria include pre-existing recognised risk factors for adverse neurodevelopmental outcome or previous exposure to general anaesthesia; or being born at less than 26 weeks gestation.

2.4. SAMPLE SIZE

The sample size was based on the 5 year follow up neurodevelopmental outcome. The WPPSI-III full scale IQ score is a standardised score with a mean of 100 and standard deviation of 15. A difference of 5 points (1/3 of a standard deviation) will be taken as the largest difference that would be acceptable to demonstrate equivalence.

The planned sample size was chosen so that if the two methods of anaesthesia really were equivalent and we assumed an expected difference of only 1 standardised score point, there was a 90% chance that a 95% confidence interval will exclude a difference of more than 5. With these assumptions, the trial would need 598 infants in total. The planned sample size of 660 allowed for 10% loss to follow-up. The enrolment target was increased to enable replacement of participants who were excluded due to major protocol violations.

Statistical Analysis Plan

3. ANALYSIS POPULATIONS

3.1. MISRANDOMISATION AND HANDLING OF STRATIFICATION ERRORS

The following cases will be considered misrandomisations and will be considered not to be part of the study population and will be excluded from all statistical analyses:

- Randomisation occurred after surgery had taken place
- · Consent withdrawn between prior to surgery
- Randomised due to technical error; no subject data collected
- The child found to fail to meet inclusion criteria or met exclusion criteria prior to surgery

Infants randomised under the incorrect stratum will be analysed under their correct stratum with no additional adjustment.

3.2. PROTOCOL VIOLATIONS

Major protocol violations include:

- surgery cancelled
- · received any sevoflurane or other volatile anaesthetic agents if allocated to awake RA arm
- received any other sedative agent if allocated to awake RA arm

Minor protocol violations include:

- variations in local anaesthetic agent
- use of opioids and/or nitrous oxide if allocated to the GA arm
- variations in volatile anaesthetic agent if allocated to the GA arm
- assessed at an age outside the planned window at 5 years

3.3. STUDY POPULATIONS AND ANALYSES SETS

Per protocol population

The PP population includes all individuals that received anaesthesia treatment as randomised and also did not encounter any major protocol violation as defined previously. Misrandomised cases will be excluded from the PP population.

Intention to treat population

The intention to treat (ITT) population includes all individuals that were randomised to one of the anaesthesia arms. Misrandomised cases will be excluded from the ITT population. Patients in the ITT population will be analysed as randomised irrespective of the actual anaesthesia treatment received.

4. OUTCOME VARIABLES

4.1. PRIMARY OUTCOME AT AGE 5 YEARS

The primary outcome is the Full Scale IQ score of the Wechsler Preschool and Primary Scale of Intelligence, Third Edition (WPPSI-III) at 5 years chronological age. Verbal, visuo-spatial and processing speed skills are incorporated into the Full Scale IQ score, which is indicative of general intellectual ability.

4.2. SECONDARY OUTCOMES AT AGE 5 YEARS

The results of the secondary outcomes will be interpreted with caution, and in the context of the results of the primary outcome and other similar secondary outcomes. Any conclusions drawn from the results of the secondary outcomes will be based on the totality of the evidence, with any indications in the direction of equivalence, benefit or harm, considered carefully.

- 1. Composite/domain scores of the WPPSI-III, specifically:
 - 1.1. Verbal IQ (VIQ; reflecting verbal intellectual skills)
 - 1.2. Performance IQ (PIQ; reflecting visuo-spatial intellectual skills)
 - 1.3. Processing Speed Quotient (PSQ; reflecting speed of cognitive processing)

Version 1 Page 6

Statistical Analysis Plan

- 2. Selected Developmental Neuropsychological Assessment, second edition (NEPSY-II) subtests to assess other cognitive skills consisting of:
 - 2.1 Attention/executive function span Sentence Repetition scaled score
 - 2.2 Attention/executive function sustained Auditory Attention combined scaled score
 - 2.3 Attention/executive function inhibitory control– Inhibition combined scaled score
 - 2.4 Attention/executive function inhibitory control Statue scaled score
 - 2.5 Verbal/language skills Word Generation scaled score
 - 2.6 Verbal/language skills Speeded Naming combined scaled score
 - 2.7 Memory & learning Memory for Names and Memory for Names Delay (combined) scaled score
 - 2.8 Social perception Affect Recognition scaled score
 - 2.9 Social perception Theory of Mind scaled score
 - 2.10 Sensorimotor skills Fingertip Tapping consisting of
 - 2.10.1 Repetitions scaled score
 - 2.10.2 Sequences scaled score
 - 2.11 Visuomotor integration Design Copy Process Total scaled score
- 3. The Wechsler Individual Achievement Test Second Edition Abbreviated (WIAT- II Abbreviated) to assess the academic skills of the child specifically
 - 3.1 Word Reading standard score
 - 3.2 Numerical Operations standard score
 - 3.3 Spelling standard score
- 4. The Children's Memory Scale (CMS) to assess
 - 4.1 Attention/executive function working memory Numbers Total scaled score
 - 4.2 Memory and learning Word Lists I (learning) scaled score
 - 4.3 Memory and learning Word Lists II (delayed) scaled score
- 5. Parent/caregiver rated scales to assess the behaviour of the children using
 - 5.1 The Global Executive Composite (GEC, T score) of the Behaviour Rating Inventory of Executive Function Preschool Version Parent Form (BRIEF-P) to measure behavioural executive abilities
 - 5.2 The Global Adaptive Composite (GAC, composite score) of the Adaptive Behavior Assessment System Second Edition (ABAS-II) to measure the child's adaptive behavior
 - 5.3 The Child Behaviour Checklist Caregiver Questionnaire (CBCL) to measure behavioural problems consisting of
 - 5.3.1 The Total Problems Score (T score)
 - 5.3.2 CBCL internalising problems T score
 - 5.3.3 CBCL externalising problems T score
- 6. Developmental issues
 - 6.1 Any developmental issue (any of the below)
 - 6.2 Child has speech or language issues / interventions*
 - 6.3 Child has psychomotor issues / interventions*
 - 6.4 Child has global developmental delay*
- 7. Behavioural disorders
 - 7.1. Any behavioural disorders (any of the below or oppositional defiant disorder)
 - 7.2. Child has been diagnosed with Attention Deficit Hyperactivity Disorder (ADHD)*
 - 7.3. Child has been diagnosed with Autism Spectrum Disorder (ASD) *
- 8. Physical disability
 - 8.1. Child has a hearing abnormality
 - 8.1.1. Child has a hearing aid*
 - 8.2. Child has a visual defect in either eye
 - 8.2.1. Child is legally blind*
 - 8.3. Child has cerebral palsy
- 9. Parents' awareness of group allocation*
- 10. Awareness of group allocation by Psychologist / Paediatrician*
- * These variables will be summarised using descriptive statistics by treatment arm only. No treatment effect or confidence intervals will be calculated.

Version 1 Page 7

Statistical Analysis Plan

4.3. OTHER SECONDARY OBJECTIVES (ALREADY REPORTED)

The trial also had the following secondary outcomes that were assessed at time points other than 5 years:

- 1. Compare a range of secondary neurodevelopmental measures between groups at 2 years (corrected). These included:
 - the cognitive, motor and language scales of the Bayley Scales of Infant & Toddler Development-III (Bayley-III)
 - social-emotional scale and adaptive behavior scale from the Bayley-III
 - the MacArthur-Bates Communicative Development Inventory
- 2. A paediatric assessment including a neurological examination to determine the presence of cerebral palsy conducted by a paediatrician blinded to the type of anaesthetic used.
- Describe the frequency and characteristics of apnoea in the postoperative period after both regional and general anaesthesia for inguinal hernia repair in infants and determine other factors associated with increased risk of apnoea.

These secondary endpoints have already been analysed when the 2-year database was locked and has been published previously (Davidson, 2016; Davidson, 2015).

4.4. OTHER PARAMETERS

Baseline variables (as reported in table 1 of 2 year outcome paper published in Lancet)

Patient and family data at 5 years of chronological age

- Family demographics as per 2 year paper.
- Age at assessment
- Location of assessment
- · Hospitalisation since hernia repair
- Number of anaesthetics since hernia repair
- · Head injury that involved the loss of consciousness
- Anv chronic illness
- List chronic illness
- Any prescribed medication for two months or longer
- Any seizures
- Height
- Weight
- Head circumference
- Arm circumference
- Any interventions for neurodevelopmental issues (speech therapy, physiotherapy, occupational therapy, psychology, other)
- Attends kindergarten, early learning or preparatory school on regular basis
- Duration of follow-up in study

5. STATISTICAL METHODOLOGY

5.1. DEMOGRAPHY AND BASELINE

Descriptive summary statistics of baseline variables as well as 5-year follow up data will be presented for both the ITT and PP populations by intervention group. For categorical data, frequencies and percentages will be provided. For continuous data, available sample size, mean, standard deviation, quartiles, minimum and maximum values will be provided.

5.2. ANALYSES OF PRIMARY OUTCOME VARIABLE

Descriptive summary statistics for the primary outcome variable at 5 years chronological age will be reported.

Version 1

Statistical Analysis Plan

Linear regression will be used to analyse the Full Scale IQ score of the WPPSI-III at 5 years. The model will include the factor variables anaesthesia arm (factor levels: GA and RA), gestational age at birth (factor levels: "182 to 209 days", "210 to 258 days" and ">= 259 days") as fixed effects and site as a random effect. If the model does not converge (e.g. because of small numbers in some sites) consideration will be given to replacing site in the model with country as a fixed effect.

The analysis will be conducted for the PP and the ITT populations. The analyses will be repeated for the subset of participants with follow-up data at 5 years as well as using multiple imputation to handle the cases lost to follow-up under the MAR assumption. The primary analysis will be based on the PP population and the multiple imputation analysis method because this is an equivalence study. A PP analysis is likely to give a more conservative estimate (in the direction of non-equivalence) of the true causal effect.

The model coefficient for the anaesthesia treatment effect (conditional mean difference) will be computed along with a two-sided 95% confidence interval. Equivalence will be accepted if this confidence interval excludes values less than -5 points and values greater than +5 points.

Loss to follow-up will be investigated by providing a table with summary statistics by treatment arm for participants who attended and did not attend the 5 year visit. Variables included in this table will include key baseline variables as well as the composite cognitive, language, motor and social-emotional score of the Bayley scales of infant and toddler development measured at the 2-year time point.

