6.1. HANDLING OF MISSING DATA

Statistical analysis approaches and imputation techniques can never compensate for or exactly reproduce missing data. Therefore, no analytical strategy exists that can minimise all bias potentially introduced by missing data. However, consistencies or inconsistencies in the results based on different strategies to handle missing data can provide support for the interpretation of the study findings and either strengthen or qualify the study conclusions.

Allowing for missing values using multiple imputation:

Assuming validity of the MAR assumption, fully conditional modelling will be used to multiply impute missing values based on variable-specific prediction models. In particular, multivariate imputation chained equations (MICE) will be used to perform imputation of missing values. Depending on the type of outcome, different link functions and model specifications will be employed to utilise the built-in imputation: predictive mean matching under a Gaussian model for continuous data, logistic regression for binary data, polytomous logistic regression for unordered categorical data and proportional odds models for ordered categorical data.

Statistical Analysis Plan

If MICE models do not converge missing values will be filled in using multivariate normal regression (MVN). These two methods have been shown to give broadly equivalent results.

A total of 20 imputed data sets will be generated based on the MICE algorithm. For each of the respective data sets, the outcome-specific effect estimate and standard error will be computed and pooled using Rubin's rules (Van Buuren, 2007).

In the analysis of the 5-year data of the GAS study, the variables used in the multiple imputation models will include baseline, post-randomisation, 2 year cognitive variables and 5 year outcome variables. The following prespecified variables will be used as predictor variables within the imputation approach (since most of these variables also have missingness, they will also be imputed where necessary):

Baseline: anaesthesia group, country, site (if possible), sex, gestational age at birth (categorised), birth weight, mother received antenatal steroids, mother's education, maternal age < 21

Surgery: need for fluid bolus for hypotension, duration of surgery, significant postoperative apnoea, age at surgery

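### The primary per-protocol model adjusts only for gestational-age band and site, leaving out baseline covariates already collected that could reduce measured selection and add some precision

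*SAP*

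**What the plan says.** **Outcome model (SAP 5.2).** For Full Scale IQ, "The model will include the factor variables anaesthesia arm (factor levels: GA and RA), gestational age at birth" are fixed effects and site is a random effect, with country as the fallback. Gestational age and site are the randomisation strata (2.1). The model is run on PP and ITT, each with multiple imputation and on children with 5-year data. The multiply imputed PP analysis is primary. The decision rule is: "Equivalence will be accepted if this confidence interval excludes values less than -5 points and values greater than +5 points".

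**Who leaves the PP set (3.2, 3.3).** There are three major violations: cancelled surgery, any volatile agent in an infant allocated to RA, and any other sedative in an infant allocated to RA. Opioids, nitrous oxide or a different volatile agent in the GA arm are minor and do not exclude.

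**Covariates at hand (6.1).** The baseline imputation variables include "site (if possible), sex, gestational age at birth (categorised), birth weight, mother received antenatal steroids", followed by mother's education and maternal age under 21. They are themselves imputed where missing.

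**Sensitivity analyses (6.2).** Complete case and multiple imputation are named. No analysis adjusts for baseline covariates beyond the strata.

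**The concern.** Adjusting for the strata suits a randomised set. The primary set here is selected after randomisation, by rules that fall mainly on one arm. If RA infants who received a volatile agent or sedative differ in expected IQ from those who did not, beyond gestational age and site, the PP contrast mixes that difference with the effect of anaesthesia.

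Section 5.2 defends PP as likely to err towards non-equivalence. One-sided exclusion can move the estimate either way. Away from zero it costs power; towards zero it makes a false equivalence claim more likely.

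Using the covariates for imputation does not deal with this. It neither adjusts the contrast among observed PP children nor brings back the excluded RA infants. Equivalence depends on the centre and the width of one confidence interval, and prognostic baseline covariates act on both.

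**Working it through.** **1. The plan's own figure.** Inputs from 2.4: "standardised score with a mean of 100 and standard deviation of 15"; margin 5; true difference taken as 1 point; "there was a 90% chance that a 95% confidence interval will exclude a difference of more than 5"; "the trial would need 598 infants in total".

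n per arm = 2 × 15² × (1.960 + 1.282)² / (5 − 1)² = 296, or 592 in total, close to 598. At 299 per arm, SE = 15 × √(2/299) = 1.227, and

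power = Φ((5 − 1)/SE − 1.96) − Φ((−5 − 1)/SE + 1.96) = 90.2%.

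Also, "The planned sample size of 660 allowed for 10% loss to follow-up": 660 × 0.9 = 594, where power is 90.0%. The plan meets its power with the unadjusted SD of 15.

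**2. Precision.** Let R² be the share of variance that the five covariates explain beyond the current terms. The SAP gives no value, so the range is assumed. SE is multiplied by √(1 − R²). With N = 598 and true difference 1:

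| R² | SE | Fall in SE | CI half-width | Power |
|---|---|---|---|---|
| 0 | 1.227 | – | 2.40 | 90.2% |
| 0.05 | 1.196 | 2.5% | 2.34 | 91.6% |
| 0.10 | 1.164 | 5.1% | 2.28 | 92.9% |
| 0.20 | 1.097 | 10.6% | 2.15 | 95.4% |

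**3. PP selection.** If a share f of the RA arm is excluded and excluded infants differ from retained ones by g IQ points (beyond gestational age and site), the mean of retained RA infants differs from that of the whole arm by f × g. The SAP gives neither f nor g; both are assumed. The sample is held at 299 per arm, since 2.4 provides for replacing infants excluded for major violations.

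| f | g | Bias | Power at true difference 1, bias away from zero | Equivalence claimed at true difference 5, bias towards zero |
|---|---|---|---|---|
| any | 0 | 0 | 90.2% | 2.5% |
| 5% | 2 | 0.10 | 88.7% | 3.0% |
| 10% | 5 | 0.50 | 81.4% | 6.0% |
| 20% | 5 | 1.00 | 68.6% | 12.6% |

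**4. How much adjustment removes.** A simulation used 330 per arm, true effect 0, a measured covariate with R² 0.2 and an unmeasured one with R² 0.1. Between 18% and 21% of the RA arm was excluded, with log-odds slopes of 0.3 or 0.5 per SD. There were 1,500 replicates; Monte Carlo error is about 1.23/√1500 = 0.03 points.

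- Exclusion unrelated to prognosis: bias about 0 with or without adjustment (0.02 and 0.03).
- Exclusion driven by the measured covariate only: 0.33 and 0.67 points fall to −0.02 and 0.04.
- Exclusion driven by both: 0.64 and 1.11 points fall to 0.25 and 0.49.

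**The case against.** **Precision is a preference, not an error.** A reader might infer that the trial is underpowered without the covariates. The plan does not support that: the model contains the randomisation strata, and 598 gives 90% power with no further adjustment. The gain is efficiency forgone. This stands.

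**The covariates are not shown to be strong predictors of IQ.** Section 6.1 lists them as imputation predictors without any correlation or R², and a variable may be listed because it predicts missingness. This stands, and is why step 2 shows a range.

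**Confounding is not shown.** A reader might infer that the PP estimate is confounded. That needs excluded infants to differ in prognosis beyond gestational age and site, and the SAP gives neither an exclusion rate nor a gap. Cancelled surgery can occur in either arm, and 3.3 requires treatment as randomised in both. A full point of bias needs steep inputs. Through mother's education alone, at an assumed 5 IQ points per SD, it takes a 0.2 SD imbalance, meaning excluded and retained infants 2 SD apart at 10% exclusion or 1 SD apart at 20%. What remains is a risk, not a demonstrated bias.

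**Safeguards exist.** The same model is run on ITT, and 5.1 tabulates baseline variables by arm for both populations. These could reveal an imbalance, but they do not correct the primary estimate, and 5.2 does not require ITT to agree with PP.

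**Adjustment has costs.** Section 6.1 says most imputation variables have missing values, so adding them to the complete-case model could drop children. It also expects convergence trouble with rare binary variables. Both points stand and shape the fix.

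**Conclusion.** The point holds as a weakness of specification. The primary contrast is exposed to selection that is partly measured, the variables that could reduce it are already collected and imputed, and no planned analysis uses them for adjustment. A later adjusted analysis would have to be reported as unplanned under 6.4.

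The size is conditional. For the assumed ranges, bias runs from nil to about 1 point and the SE reduction from 2.5% to 10.6%. Adjustment deals only with the measured part: in the simulation about 0.25 to 0.49 points remained when an unmeasured factor also drove exclusion. The documents do not show that the sample size is wrong, that the covariates are strong predictors or that the PP estimate is biased. The change is worth making because it is cheap and must be fixed in advance to carry weight.

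**What to change.** - **Primary model (5.2).** Add sex, birth weight, mother's education, maternal age under 21 and antenatal steroids as fixed effects in the multiply imputed PP and ITT models for Full Scale IQ. Use only these baseline variables, not the surgical or later ones listed in 6.1.
- **Sensitivity analysis.** Keep the model with arm, gestational age and site on the same imputed data.
- **Complete-case analysis.** Define completeness by the outcome alone and keep the strata-only model, so that no child is dropped for a missing covariate.
- **Convergence (6.1).** The five covariates must then stay in the imputation model for congeniality, which may add to convergence problems. State that if a low-prevalence binary covariate prevents convergence, it is dropped from both the imputation and the analysis model.
- **Cross-references.** Sections 5.3 and 6.3 refer back to 5.2. State which model they use, so that the change is not inherited by accident.

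The cost is SAP wording and a somewhat more demanding imputation model. No new data are needed.

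### Equivalence is accepted on the per-protocol interval alone, although the mainly one-arm exclusions mean its conservative direction cannot be relied on; requiring ITT to agree is a cheap improvement

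*SAP*

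**What the plan says.** SAP 5.2 runs the primary model in the PP and the ITT populations, each with multiple imputation and on children with 5-year data. It then names one of these as decisive: "The primary analysis will be based on the PP population and the multiple imputation analysis method because this is an equivalence study". The supporting reason is "A PP analysis is likely to give a more conservative estimate (in the direction of non-equivalence) of the true causal effect". Equivalence is accepted if the two-sided 95% interval for the treatment coefficient excludes values beyond 5 points in either direction. ITT has no part in that rule, and the SAP does not say how a disagreement between PP and ITT would be read.

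SAP 3.2 lists three major violations. One, cancelled surgery, can occur in either arm. The other two are "received any sevoflurane or other volatile anaesthetic agents if allocated to awake RA arm" and "received any other sedative agent if allocated to awake RA arm". The listed drug deviations in the general anaesthesia (GA) arm (opioids, nitrous oxide, a different volatile agent) are minor and do not remove the infant from PP.

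SAP 3.3 adds a condition that applies to both arms: PP members must have had the anaesthetic to which they were randomised. A GA infant given only a regional block would therefore also be excluded.

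**The concern.** The usual argument for PP in an equivalence trial is that crossover dilutes the ITT contrast and pulls it toward zero. That argument is secure only when exclusion is unrelated to prognosis. Here most exclusions can be expected among RA infants who were given a volatile or sedative agent, which is an event after randomisation. GA infants of the same kind cannot be recognised and stay in. The retained RA infants may then differ in expected IQ from the GA infants they are compared with.

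Multiple imputation handles loss to follow-up within the PP set and does not bring excluded infants back. Adjustment for gestational age and site removes only the part of the selection that those factors explain. The trial's one equivalence decision thus rests on a comparison that is no longer fully randomised, defended by a statement about the direction of bias that the design does not secure.

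**Working it through.** **Inputs from SAP 2.4 and 5.2.** The outcome is a "standardised score with a mean of 100 and standard deviation of 15". The margin: "A difference of 5 points (1/3 of a standard deviation) will be taken as the largest difference that would be acceptable to demonstrate equivalence". For the planned difference, "we assumed an expected difference of only 1 standardised score point". Power is 90% with a two-sided 95% interval, and 598 evaluable infants are stated, or 299 per arm.

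**The plan's own figure.** n per arm = 2 × 15² × (1.960 + 1.282)² / (5 − 1)² = 296, or 592 in total. Allowing for both tails gives 298 per arm, or 596. The stated 598 is reproduced, so the sample size contains no arithmetic error.

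**Precision.** SE = 15 × √(2/299) = 1.227. If the analysis estimates a difference D, then

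P(equivalence) = Φ((5 − D)/SE − 1.96) + Φ((5 + D)/SE − 1.96) − 1.

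At D = 1 this is 90.2%, and at D = 5 it is 2.5%.

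**Bias model (assumed).** Let f be the share of RA infants excluded, d the expected IQ of retained minus excluded infants under the same anaesthetic, and δ the true RA − GA difference. Suppose that excluded RA infants in effect received GA and that no GA infants are excluded. Writing μ for the mean of the retained type under GA:

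- GA mean = μ − f·d; retained RA mean = μ + δ; so the PP difference = δ + f·d.
- Mean of all RA infants = μ − f·d + (1 − f)·δ; so the ITT difference = (1 − f)·δ.

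The SAP gives neither f nor d. The ranges used are f = 10-20% and |d| = 5-10 points.

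**False equivalence at |δ| = 5 when selection opposes the effect** (exclusions replaced, so 299 per arm):

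| f | Gap | PP difference | PP false equivalence | ITT difference | ITT false equivalence |
|---|---|---|---|---|---|
| any | 0 | 5.0 | 2.5% | 5(1 − f) | as below |
| 10% | 5 | 4.5 | 6.0% | 4.5 | 6.0% |
| 10% | 10 | 4.0 | 12.6% | 4.5 | 6.0% |
| 20% | 5 | 4.0 | 12.6% | 4.0 | 12.6% |
| 20% | 10 | 3.0 | 37.1% | 4.0 | 12.6% |

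For example, at D = 3: (5 − 3)/1.227 − 1.96 = −0.33, and Φ(−0.33) = 37.1%; the other tail adds nothing visible.

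**Direction.** PP moves toward equivalence if GA is worse and the excluded infants have higher expected IQ, or if RA is worse and they have lower expected IQ. With the opposite signs it moves away. At δ = 1, a bias of 0.5, 1 or 2 points away from zero cuts P(equivalence) from 90.2% to 81.4%, 68.6% or 37.1%.

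**Joint rule (simulated, both intervals within ±5, same model).**

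- True difference 5, f = 20%, 10-point gap: false equivalence falls from about 35% under PP alone to about 12%. Runs with 330 per arm gave about 36% to between 13% and 14%.
- True difference 5, f = 20%, 5-point gap: about 12.6% to 10.2%.
- True difference 5, no selection: stays at 2.5%, where ITT alone gives about 13% at f = 20%.
- True difference 1, no selection, f = 20%: power goes from 89.2% to 88.8%.
- True difference 1, f = 20%, 10-point gap moving PP away from equivalence: about 37% under either rule.

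**The case against.** The strongest defence is that PP as primary was a deliberate and coherent choice. The question is GA against awake RA without sedation. A GA infant given nitrous oxide or another volatile agent still had general anaesthesia, while an RA infant given a volatile agent no longer had the RA condition. SAP 2.4 says that enrolment was raised to replace major violators. ITT is prespecified with the same model and imputation, and SAP 5.1 tabulates both sets by arm, so disagreement would be visible. All of this stands.

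Three stronger readings are tempting, and the document does not support them.

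- *That the conservative property is false.* The SAP says only that it is likely. With no selection, or with lower expected IQ among excluded infants and GA worse, PP is the more conservative set. Nothing in the SAP indicates which sign applies. The power losses shown above are shifts toward non-equivalence, which is what the SAP sentence predicts, so they do not count against it.
- *That only RA infants can leave the PP set.* The list in 3.2 is asymmetric, but the as-randomised condition in 3.3 applies to both arms.
- *That ITT should replace PP, or that PP should be narrowed to children with no later anaesthetic.* ITT is itself diluted. In the table PP does worse than ITT only when the gap exceeds the 5-point true difference; at a 5-point gap the two are equal. Narrowing PP by later exposure would add another selection after randomisation.

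The sizes are also illustrative: both f and the gap are assumed, and adjustment for gestational age would remove some of the selection.

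**Conclusion.** The point holds in limited form. The acceptance rule rests on PP alone, no rule covers disagreement with ITT, and the listed drug-related exclusions bear on one arm. PP protects against dilution but is open to selection in either direction, so its conservative direction cannot be relied on. ITT is unselected but diluted, so neither set suffices by itself.

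Under the assumed inputs, with selection opposing the effect, false equivalence at a true 5-point difference is about 6-37% under PP alone and about 6-13% under ITT alone, against a nominal 2.5%. These figures show what could happen and do not estimate what did. The matter should be fixed because the remedy costs so little; it does not invalidate the design.

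**What to change.** In SAP 5.2, replace the acceptance rule with wording such as: *Equivalence will be concluded only if the two-sided 95% confidence intervals from both the PP and the ITT multiple-imputation analyses lie within −5 to +5 points.* Replace the sentence on conservatism with: *The PP analysis avoids dilution by crossover, but may be biased in either direction by exclusions made after randomisation.*

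The change is to wording only, since both analyses are already planned. The price is about half a percentage point of power when there is no selection. The joint rule helps most when the gap is large and only modestly at a 5-point gap. It does not bring false equivalence back to 2.5% under selection and cannot recover power that selection has removed.
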